15.1.6 Duration of Confirmed Response (RECIST 1.1) - Expansion Part

Duration of confirmed response (DoR) is defined as the number of weeks from the first documentation of confirmed objective tumor response (CR or PR) to the date of first PD or death. DoR will be analyzed using the same statistical methodology as PFS and the same censoring rules based on the FDA guideline, see section 15.1.4. DoR will be presented using confirmed responses only. Both the response assessments from the investigator will be presented.

15.1.7 Time to RECIST 1.1 and CA-125 combined response (Ovarian cancer only) – Expansion Part

Time to first RECIST 1.1 and CA-125 combined response (see Table 5 above) will be presented using the same statistical methodology as for ToR. CA-125 evaluation criteria (see section 15.1.2) should be fulfilled for CA-125 response evaluation, but not for RECIST 1.1 response evaluation (hence if they are NE based on CA-125, ovarian subjects are considered non-responder for CA-125 before defining the combined output). Both the response assessments from the investigator will be presented. The analysis will be performed for confirmed responses based on RECIST 1.1 only.

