### 4.5 Secondary Endpoints

- Safety laboratory parameters (hematology and biochemistry).
- PK parameters (clearance, volume of distribution and area-under-the-concentration-time curve [ $AUC_{0-Clast}$  and  $AUC_{0-\infty}$ ], maximum concentration [ $C_{max}$ ], time of  $C_{max}$  [ $T_{max}$ ], pre-dose values, and half-life of enapotamab vedotin and free toxin [MMAE]).
- Immunogenicity of enapotamab vedotin (anti-drug antibodies).

Document Name: GCT1021-01 Protocol

Document Number: TMF-03326

Version: 11.0

---

- Anti-tumor activity measured by tumor shrinkage (based on computerized tomography [CT]-scan evaluations), as well as change in CA 125 in patients with ovarian cancer and change in prostate specific antigen (PSA) in patients with castration-resistant prostate cancer (CRPC).
- Objective Response, Progression-Free Survival (PFS), Duration of Response (DoR) and Overall survival (OS).
- Axl expression in the tumor biopsy.

[figure not shown]

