***For the following conditions in Expansion Cohorts 1-8, the sponsor medical officer's approval of enrolment is needed:***

- if documented progression has not been on measurable disease (i.e., symptomatic progression)

Document Name: GCT1021-01 Protocol

Document Number: TMF-03326

Version: 11.0

2. Patients must have measurable disease according to Response Evaluation Criteria In Solid Tumors (RECIST) version 1.1.

- A minimum of one lesion  $\geq 10$  mm (or twice the slice thickness if slices are not 5 mm thick) in the longest diameter (LD) from a non-irradiated area.
  - Lymph nodes lesion  $\geq 15$  mm in the shortest diameter from a non-irradiated area.
  - If target lesion(s) are located within previously irradiated area patients can be enrolled if:
    - target lesions have not been irradiated within the last 3 months
    - there has been demonstrated progression in the “in field” target lesion and after sponsor acceptance
- In the dose escalation part, patients with ovarian cancer can be included based on CA 125 positivity according to the Gynecologic Cancer Intergroup Guideline; only if they have a pretreatment sample that is at least twice the upper limit of the reference range and within 2 weeks before starting the treatment.

Note: Patients are not evaluable by CA 125 if they have received mouse antibodies (unless the assay used has been shown not to be influenced by human anti-mouse antibody) or if there has been medical and/or surgical interference with their peritoneum or pleura during the previous 28 days (e.g., paracentesis).

3. A) In the dose escalation part all patients must provide a tumor tissue sample (Formalin Fixed Paraffin Embedded (FFPE) blocks / slides) from archival tissue or fresh biopsy collected before Cycle 1, Visit 1, preferably derived from advanced disease stage. B) In the expansion part all patients must provide a mandatory fresh biopsy (FFPE tissue blocks/slides) at screening (aspirates are not acceptable) which contains tumor tissue and is taken after failure/stop of last prior treatment. Documentation of the fresh FFPE biopsy shipment must be submitted to the Sponsor as a part of eligibility package prior to administration of first dose of enapotamab vedotin. In case it is not feasible to meet the required criteria for fresh tumor biopsy, the sponsor medical officer’s approval of enrollment is needed. Furthermore, the latest available archival tumor tissue sample must be collected if available.

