### **10.3.11 Axl Expression**

Axl expression measurements will be listed and summarized. Furthermore, association between degree and intensity of Axl expression and biologic activity as measured by tumor burden, CA 125 and response will be investigated using correlation and logistic regression analysis correspondingly.

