#### **10.4.3 Duration of Response**

DoR is defined as the number of days from the first documentation of objective tumor response (CR or PR) to the date of first PD or death. DoR will be analyzed using the same statistical methodology as PFS.

Document Name: GCT1021-01 Protocol

Document Number: TMF-03326

Version: 11.0

---

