4.9 Changes to Protocol

Changes compared to protocol final version 10.0, dd. 9 December 2019:

Table 4 Evaluation of Response in section 15.1 of this SAP has been updated by clarifying the definition of not-evaluable (NE).

Subgroup analysis for Cohort 2 (up to 2 lines of prior therapy versus more than 2 lines of prior therapy within the 2.2 mg/kg dose level), Age (age<65 years and age ≥65 years), Gender, Histology: squamous versus non-squamous, ECOG performance score (0 versus 1), smoking status ((current smoker, past smoker, non-smoker), amendment 6 period (inclusion before amendment 6, after amendment 6), best response to latest regimen (CR, PR, SD, PD) and histology results (Chondrosarcoma vs other) – Cohort 5 are added.

IRC tumor assessments are not presented, the BOR and CBOR based on IRC are listed only.

PSA results (when available) and urinalysis results will only be listed.

The Safety Set is updated by removing the condition to have a valid post-baseline safety assessment as it is considered appropriate to keep all exposed subjects in the safety set to align with ICH guidelines.

Additional adverse events tables are added for completeness.

One additional analysis set is added: PK analysis set.

The interim analysis at the end of the dose-escalation part is removed as data from the dose-escalation and expansion part will be presented together as described in section 4.2.

5. Trial Subjects

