15.7 Tumor Axl-Expression – Expansion Part

Tumor Axl-expression measurements will be listed and summarized descriptively (by tumor type, by fresh/archived biopsy, by last treatment given before the biopsy was taken based on pre-defined groups).

The following parameters will be included:

- H-score quantified based on Axl positivity in
 - i) membrane,
 - ii) cytoplasm,
 - iii) membrane or cytoplasm (higher value of the two)

Descriptive statistics (actual values and percent change from baseline) will be presented to summarize the H-score parameters (for membrane and cytoplasm) at baseline and over time (archival and fresh screening results, cycle 2 and end-of-treatment results).

Mean-se plots over time will be done for the actual values and percent change from baseline.

TPL N°: eTPL SA-02-01 TPL Version: 02

Of SOP SA-02.08 TPL Effective Date: 31 Mar 2016

Box-and-whisker plot showing baseline expression of Axl (H-score) across cohorts will also be presented.

15.8	

16. Pharmacokinetics

The calculation of the pharmacokinetic endpoints will be performed by A separate PK analysis plan will be written by to describe the planned non-compartmental PK analyses for this trial.

PK concentrations and individual PK parameters will be analyzed on the PK Analysis set.

Individual plasma/serum concentration time curves of enapotamab vedotin (conjugated), enapotamab vedotin (total) and free toxin (MMAE), including information on actual dose, will be presented for all subjects in the PK set for the escalation part. All available data will be shown in these figures. The value <LLoQ will be replaced by the numerical LLoQ value divided by 2 and mentioned in a footnote.

The plasma/serum concentrations will also be summarized descriptively over time according to the schedule specified in section 8.1 of the protocol final version 10.0, dd. 9 December 2019. The number of subjects with an imputed LLoQ value will be added.

Mean-se graphs for the plasma/serum concentrations by cycle and dose level will be presented both with and without error bars.

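### The SAP summarises duration of response and tumour Axl expression for the expansion part only, although the protocol plans both as secondary endpoints without that limit, and SAP 4.9 does not record the change

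*SAP*

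**What the plan says.** **Protocol.** Section 4.5 names DoR alongside objective response, PFS and OS, and separately lists "Axl expression in the tumor biopsy". Neither is tied to one part of the trial. Section 10.3.11 states that "Axl expression measurements will be listed and summarized". Section 10.4.3 begins "DoR is defined as the number of days from the first documentation of objective tumor response" and analyses DoR by the PFS method. Section 10.3 makes the Full Analysis Set, which is every exposed patient, the default. Section 10 has results presented separately for the two escalation arms and the expansion. Inclusion criterion 3 adds: "In the dose escalation part all patients must provide a tumor tissue sample"; this may be archival or fresh.

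**SAP.** Section 4 reports both trial parts by default, unless something else is specified. For these two endpoints something else is specified:

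- DoR: section 15.1.6 is headed "Duration of Confirmed Response (RECIST 1.1) - Expansion Part". Table 14.02.06 and Graph 14.02.04 are marked for the expansion only.
- Axl: section 15.7 says "Tumor Axl-expression measurements will be listed and summarized descriptively", under a heading limited to the expansion. Tables 14.02.10.a and 14.02.10.b (H-score in membrane and in cytoplasm) are ticked for the expansion only. The baseline percentage of Axl-positive cells in section 7 carries the same limit.

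Section 4.9, introduced by "Changes compared to protocol final version 10.0", records neither restriction.

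**The concern.** Two secondary endpoints are narrowed between protocol and SAP without being logged. SAP 4.9 does log comparable reductions: IRC results reduced to a listing of best response, and PSA and urinalysis listed only. Someone relying on 4.9 would conclude that DoR and Axl are summarised as the protocol planned.

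Axl matters more. Protocol 4.2 sets the objective of evaluating Axl expression in a mixed population with solid tumours. The escalation part draws on ovary, cervix, endometrium, thyroid, NSCLC and melanoma including uveal (inclusion criterion 1). Protocol Appendix I singles out thyroid cancer for the highest Axl expression, and thyroid has no dedicated expansion cohort. Escalation patients were required to give tissue, yet the planned summary of what that tissue showed leaves them out.

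**Working it through.** The SAP gives no figure to reproduce, so the check sets the texts side by side. Arithmetic only shows scale.

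**1. Scope of each endpoint named in protocol 4.5**

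| Endpoint | Protocol limit by part | SAP table for escalation? |
|---|---|---|
| Objective response | none | yes (14.02.01.01, 14.02.01.02) |
| PFS | none | yes (14.02.04.01) |
| OS | none | yes (14.02.08.01) |
| DoR | none | no (14.02.06, expansion only) |
| Axl expression | none | no (14.02.10.a/b, expansion only) |

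Of the four RECIST or survival endpoints, DoR is the only one not tabulated for escalation.

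**2. Is the restriction recorded or reversed elsewhere?** SAP 4.9 has no entry for either endpoint. The SAP addendum repeats disposition, PFS, OS, selected safety outputs and listings, and restores neither summary.

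**3. What remains for escalation?** Listing 16.02.02.02.01 includes DoR and Listing 16.02.02.06 gives Axl values. Neither title limits the trial part, and SAP 20.3 asks for all available data. Table 14.01.07 (biopsy information) is ticked for both parts. The loss is therefore of summaries, not of data.

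**4. Patients affected, Axl**

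- Planned maximum (protocol 3.4): 41 + 36 = 77. Check: 77 + 349 in expansion = 426, the stated total. Share: 77/426 = 18%.
- Expected (protocol 3.2): 28 + 17 = 45. Share of the same planned total: 45/426 = 11%.

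**5. Patients affected, DoR**

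Only responders count. The documents give no escalation response rate. As an illustration I take 10%, the null rate used for most expansion cohorts in protocol 10.2.3:

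- Expected: 45 × 0.10 = 4.5 responders. Maximum: 77 × 0.10 = 7.7.
- By dose level: SAP 4 presents seven 1Q3W and four 3Q4W levels, 11 in all. 4.5/11 = 0.4 and 7.7/11 = 0.7, so fewer than one responder per level.
- Pooled per schedule: 1Q3W from 28 × 0.10 = 2.8 to 41 × 0.10 = 4.1; 3Q4W from 17 × 0.10 = 1.7 to 36 × 0.10 = 3.6.

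A DoR summary by dose level would add almost nothing to the listing. Pooled per schedule, it is the most that can usefully be shown.

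**The case against.** The strongest reply is that the restriction is open and sensible. The SAP allows exceptions to its both-parts rule and states these in section headings and table shells. The protocol leaves analysis details to the SAP. Escalation tissue may be archival, and protocol 8.5.10 calls Axl expression dynamic and heterogeneous. Escalation responders will be few.

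Part of this stands. Small numbers could justify dropping a DoR table, but the SAP does not give that reason, and it would not explain the Axl restriction, because tissue comes from all patients. Archival tissue is no obstacle either: SAP 15.7 already splits Axl by fresh or archived biopsy. Leaving details to the SAP does not remove the need to log a narrowed secondary endpoint in the section meant for that.

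A reader might infer more than the documents support:

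- *That escalation tissue is never summarised.* Table 14.01.07 covers biopsy type, location, timing and evaluability for escalation. SAP 15.8, most of section 18 and many output titles are redacted, so an exploratory escalation Axl output cannot be excluded.
- *That DoR alone was dropped from the response outputs.* Time to confirmed response, combined RECIST/CA-125 response, time to combined response and the swimlane plots are also expansion-only. The narrower statement about the four endpoints in protocol 4.5 is the one that holds.
- *That durable escalation responses can be seen only in listings.* Spider plots marked by best response (SAP 15.4; Graph 14.02.08.01) and PFS curves cover escalation.
- *That cervix, endometrium and thyroid have no Axl summary at all.* Cohort 6 can enrol them after PD-1/PD-L1 failure, preferably no more than 8 per tumour type, and 15.7 summarises by tumour type. Uveal melanoma is outside the histologies listed for Cohorts 3 and 4, and melanoma enters Cohort 6 only with known AXL amplification.

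**Conclusion.** The point holds and is minor. Two secondary endpoints planned without limit by trial part are summarised for the expansion only, and the SAP's list of changes does not say so. For Axl, about 45 expected and at most 77 of about 426 patients fall outside every visible summary of results. For DoR, perhaps 4 to 8 responders do, under the illustrative 10% rate; the true number could be lower or higher. The Axl half justifies a change to the outputs. The DoR half alone would add little.

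Three assumptions apply. The enrolment figures are planned, not actual. The redacted outputs contain no escalation Axl summary. And SAP 4.9 compares with protocol version 10.0, while the text available is version 11.0; its summary of changes names sections 10, 10.7 and 10.8 in the statistics chapter but not 4.5, 10.3.11 or 10.4.3, so I take those three to be unchanged in substance.

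**What to change.** Run Tables 14.02.10.a and 14.02.10.b for the escalation part as well, by tumour type and by fresh or archival tissue, as 15.7 already does for the expansion. Add one DoR summary of confirmed escalation responders, pooled within each schedule and read descriptively. Record in SAP 4.9 any restriction that is kept, with its reason. The addendum says that data to the March 2021 cut-off have already been reported, so the extra outputs could go into the report addendum.

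The cost is a little more programming, since the expansion programs exist. The downside is small groups, particularly by tumour type, that need cautious reading.

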15.1 Response

The response results from the dose-escalation part and the expansion part will be presented using summary statistics.

Response will be defined according to RECIST 1.1. For subjects with ovarian cancer (Cohort 7) the response will be defined on the combination of the response according to RECIST 1.1 and CA-125 (see below in section 15.1.2).

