15.1.1 Response according to RECIST 1.1

[figure not shown]
Response in solid tumor cancers will be assessed in accordance with the RECIST criteria version 1.1^2 .

Table 4. Evaluation of Response

Target Lesions	Non-target Lesions	New Lesions	Response
CR	CR	No	CR
CR	Non-CR/Non-PD	No	PR
CR	Not evaluated	No	PR
PR	Non-PD or not all evaluated	No	PR
SD	Non-PD or not all evaluated	No	SD
Not all evaluated	Non-PD	No	NE
PD	Any	Yes or No	PD

TPL N°: eTPL SA-02-01 TPL Version: 02 Of SOP SA-02.08

TPL Effective Date: 31 Mar 2016 Approved in Vault: 6/30/2021

Any	PD	Yes or No	PD
Any	Any	Yes	PD

Confirmation:

PR and CR: changes in tumor measurements that are confirmed* by repeat assessments performed no less than four weeks after the criteria for response are first met are called confirmed responses. Onset of PR or CR without such confirmation is called unconfirmed.

SD: follow-up measurements must have met the SD criteria at least once and for a minimum time period of 6 weeks (\pm 7 days) after first treatment.

In the dose-escalation, response evaluation will be performed by the investigator. In the expansion, response evaluation will be performed by the investigator as well as a group of external medical experts, the independent review committee (IRC). Each subject will be assigned one of the following categories for each assessment:

- 1) CR,
- 2) PR,
- 3) SD,
- 4) PD, or
- 5) Not Evaluable (NE)

The best overall response is the best response recorded from the start of the treatment until disease progression/recurrence.

A subject is defined as an objective responder if he/she has a best overall response assessment of CR or PR.

Subjects in response categories 3, 4 and 5 (SD, PD or NE) are considered as non-responders.

Subjects with a best overall response assessment of CR, PR or SD are considered to be in disease control.

Confirmed* responses and all responses (including confirmed and unconfirmed responses) will be presented separately for the objective response (yes/no) and disease control (yes/no) parameters.

- [* The following sequences (assessments over time) will be counted as confirmed response:
 - CR-CR = CR confirmed
 - PR-PR = PR confirmed
 - PR-CR = PR confirmed

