15.1.2 Response according to CA-125

Subjects with ovarian cancer will also be evaluated according to CA-125.

A CA-125 response (PR) is defined as at least a 50% reduction in CA-125 levels from a pretreatment sample. The response must be confirmed and maintained for at least 28 days. Subjects can be evaluated according to CA-125 only if they have a pretreatment sample that is at least twice the upper limit of the reference range and within 2 weeks before starting the treatment.

More information on the rules that apply to the CA-125 data is available in section 10.4 of the protocol final version 10.0, dd. 9 December 2019.

The date when the CA-125 level is first reduced by 50% is the date of the CA-125 response.

To calculate response, an analysis should be used that includes all subjects with an initial CA-125 level of at least twice the upper limit of the reference range as eligible and evaluable.

In addition, as a separate analysis, those subjects who have a CA-125 response and whose CA-125 level falls to within the reference range can be classified as CA-125 complete responders. Subjects who have a fall of CA-125 to within the reference range but whose initial CA-125 was less than twice the upper limit of the reference range have not had a CA-125 response and cannot therefore be classified as a CA-125 complete responder.

The best overall response for both parameters (CA-125 response and CA-125 complete response) will be presented.

15.1.3 Response according to RECIST 1.1 and CA-125 combined (Ovarian cancer only) – Expansion Part

For subjects with ovarian cancer in the expansion part, responses will also be evaluated and reported according to RECIST 1.1 in combination with CA-125 as defined by the Gynecological Cancer Intergroup³ (see table 5).

TPL N°: eTPL SA-02-01 TPL Version: 02 Of SOP SA-02.08

OF SOP SA-02.08

TPL Effective Date: 31 Mar 2016

Approved in Vault: 6/30/2021

Table 5. Best Overall Response in Subjects with Initial Measurable Disease and Evaluable by CA-125, combining both criteria

Non Target #	New Lesion	CA-125	Overall Best Response	Best
CR	No	Normal	CR	RECIST 1.1 response
Non-CR Non-PD	No	Not PD	PR	for CR and PR also requires
CR	No	PR but not normal	PR	it to be confirmed and
NE	No	PR	PR	maintained for
Non-PD or NAE	No	Not PD	PR	at least 28 days if response
Non-PD	No	PR	PR	is primary end point
PD or New >28 days from		PR	PR	
CA-125 PR *	:			
Non-PD	No	PR	PR	
Non-PD or NAE	No	Not PR and not PD	SD	
•	ys from	PR	PD	

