CA-125 PR*	T			
Any	Yes or No	Any	PD	
PD	Yes or No	Any	PD	
Any	Yes	Any	PD	
Any	Yes or No	PD	PD	
	Target # CR Non-CR Non-PD CR NE Non-PD or NAE Non-PD lew > 28 day CA-125 PR * Non-PD Or NAE ew ≤ 28 day CA-125 PR* Any PD Any	Target # Lesion CR No Non-CR No Non-PD CR No NE No Non-PD No or NAE Non-PD No lew >28 days from CA-125 PR * Non-PD No or NAE ew ≤ 28 days from CA-125 PR* Any Yes or No Any Yes	Target # Lesion CR No Normal Non-CR No Not PD CR No PR but not normal NE No PR Non-PD No Not PD Iew > 28 days from PR CA-125 PR * Non-PD No Not PR Non-PD No PR Non-PD No PR CA-125 PR * Any Yes or No Any Any Yes or No Any Any Yes or No Any Any Yes or No Any	Target # Lesion Response CR No Normal CR Non-CR Non-PD No Not PD PR CR No PR but not normal PR NE No PR PR Non-PD No Not PD PR Non-PD No PR PR PR PR PR CA-125 PR * No Not PR and not PD Non-PD No Not PR and not PD SD ew ≤ 28 days from CA-125 PR* PR PD Any Yes or No Any PD Any Yes or No Any PD

 $[\]sim$ target lesions include up to 5 measurable lesions (2 per organ) as defined by RECIST 1.1.

Source: Definitions for Response and progression of ovarian cancer incorporating RECIST 1.1 and CA-125 agreed by the Gynaecological Cancer Intergroup (GCIG) – Rustin et All^3

TPL N°: eTPL SA-02-01 TPL Version: 02 Of SOP SA-02.08

TPL Effective Date: 31 Mar 2016

Approved in Vault: 6/30/2021

[#] non-target lesions include ascites and peritoneal thickening which are not measurable according to RECIST 1.1.

^{*} subjects who have a CA 125 response that occurs more than 28 days from PD according to RECIST 1.1 are considered a PR, according to best response, but PD if the RECIST 1.1 PD is within 28 days of CA 125 response. § the minimum time interval between 2 measurements for classification as stable disease is 6 weeks (± 7 days).

NE, Not evaluated; NAE, not all evaluated.

Best overall responses by investigator will be tabulated as in the example of the guideline³.

Progression or Recurrence based on serum CA 125 levels (PD in the table above) will be defined on the basis of a progressive serial elevation of serum CA 125, according to the following criteria:

A. Subjects with elevated CA-125 pretreatment and normalization of CA-125 must show evidence of CA-125 greater than, or equal to, two times the upper normal limit on two occasions at least one week apart or

Version: 4.0

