15.1.5 Time to Confirmed Response according to RECIST 1.1 - Expansion

Time to Confirmed Response (TOR) is defined as the number of weeks from date of first IMP administration to the date of first response (CR or PR) according to RECIST 1.1. Only responders will be included in the analyses (no censoring). TOR will be analyzed using the

Page 25 of 46 TPL N°: eTPL SA-02-01

TPL Effective Date: 31 Mar 2016 Approved in Vault: 6/30/2021

Of SOP SA-02.08

same statistical methodology as PFS. For these analyses, only confirmed responses will be used. Both the response assessments from the investigator will be presented.

Version: 4.0

The time to event graph of TOR will represent only confirmed responders and will start from the bottom-left corner (no responders) to the top-right corner.

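### Read literally, the last sentence of SAP 15.1.7 leaves CA-125-driven responders out of the time-to-combined-response analysis in Cohort 7; the SAP should say whether it means that

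*SAP*

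**What the plan says.** SAP 15.1 states that for Cohort 7 "the response will be defined on the combination of the response according to RECIST 1.1 and CA-125". Section 15.1.3 gives the combination rule in Table 5.

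Section 15.1.7 then sets the time-to-event version: "Time to first RECIST 1.1 and CA-125 combined response (see Table 5 above) will be presented using the same statistical methodology as for ToR". The method it borrows, in 15.1.5, takes responders only, applies no censoring, and already uses confirmed responses only.

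Section 15.1.7 also says how patients who cannot be evaluated by CA-125 enter the calculation: "ovarian subjects are considered non-responder for CA-125 before defining the combined output". It closes with: "The analysis will be performed for confirmed responses based on RECIST 1.1 only".

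The planned outputs are Table 14.02.07 and Graph 14.02.05, both titled as combined response. The matching response tables are 14.02.03.01 (confirmed) and 14.02.03.02 (all responses).

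**The concern.** Table 5 can make a patient a combined responder through CA-125 when the scans show no RECIST response. If the closing sentence of 15.1.7 admits only confirmed RECIST responses, such a patient is not a responder for this analysis. Because non-responders are left out rather than censored, the patient disappears from the output.

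The combined output would then hold no Cohort 7 patient beyond the confirmed RECIST responders already shown in Table 14.02.05, and its responder count could differ from that in Table 14.02.03.01. The patients lost would be those whose response was picked up by the marker, which is sampled every 3 weeks, rather than by the scan, which is done every 6 weeks. The times that remain could therefore be later than those of the full set of combined responders.

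**Working it through.** The plan attaches no figure to this analysis, so there is nothing to reproduce. The check is mainly one of logic.

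**Which Table 5 responders lack a RECIST response?**
- SAP 15.1.1 on RECIST status: "Subjects in response categories 3, 4 and 5 (SD, PD or NE) are considered as non-responders".
- Table 5 as extracted has 8 rows that give a combined CR or PR. Five of them need a CA-125 PR.
- One row is explicit: progression or a new lesion more than 28 days from the CA-125 PR gives a combined PR. The footnote to Table 5 repeats this: "subjects who have a CA 125 response that occurs more than 28 days from PD according to RECIST 1.1 are considered a PR".
- Two further rows (non-target disease not progressing, no new lesion, CA-125 PR) probably also describe patients whose target lesions are not in CR or PR. A target PR with non-progressing non-target disease already earns a combined PR when CA-125 is merely not PD, so these rows would otherwise be redundant. This is inference, because the target-lesion column was lost when the text was extracted.
- So 1 of 8 response rows certainly, and about 3 of 8 probably, define combined responders with no RECIST response.

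**What does the closing sentence do to them?**
- Literal reading: no confirmed RECIST response, so not a responder here, so absent under the 15.1.5 method.
- Alternative reading: only the RECIST component has to be confirmed. The CA-125 component has its own rule in 15.1.2 ("The response must be confirmed and maintained for at least 28 days"), so these patients stay in.

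**How many patients?** The documents do not say. For illustration, assume a RECIST rate of 15% (the Cohort 7 null value in Protocol 10.2.3) and a combined rate of 20% to 35%. Cohort 7 has a target of 22 patients and a maximum of 37.
- Patients omitted = N × (combined rate − RECIST rate).
- N = 22: 22 × 0.05 = 1.1 to 22 × 0.20 = 4.4, about 1 to 4.
- N = 37: 37 × 0.05 = 1.9 to 37 × 0.20 = 7.4, about 2 to 7.
- Share of combined responders omitted = 1 − RECIST rate / combined rate: 1 − 0.15/0.20 = 25%; 1 − 0.15/0.25 = 40%; 1 − 0.15/0.35 = 57%.
- If nobody responds through CA-125 alone, the two rates are equal and the effect is zero.

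**Does the median move?** CA-125 is taken at Visit 1 of each 3-week cycle (Protocol Table 11), so the earliest post-treatment date is Day 21 + 1 = 22. The first scan is due at 6 weeks, Day 42 + 1 = 43, with a window of ±7 days. Put every CA-125-only responder at Day 22 and every RECIST responder at Day 43:

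| Share omitted | Median, all combined responders | Median, literal rule | Shift |
|---|---|---|---|
| 25% | Day 43 | Day 43 | 0 |
| 40% | Day 43 | Day 43 | 0 |
| 57% | Day 22 | Day 43 | 21 days |

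In this picture the median moves only when more than half of the combined responders are omitted.

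**The case against.** The strongest reply is that the sentence has a sensible purpose. The SAP reports combined response twice, confirmed and all, so a time-to-response section has to say which it uses. The note beside Table 5 ties confirmation to RECIST CR and PR, and CA-125 response carries its own 28-day rule, so only RECIST would need the qualifier. On that reading the instruction about patients not evaluable by CA-125 has a purpose; on the literal reading it has almost none. This is plausible, and it stands as a possible reading. It does not settle the matter: the SAP nowhere says it, and 15.1.5 already limits the borrowed method to confirmed responses.

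A reader might infer that CA-125 responders are definitely removed, that the counts will not match, or that the reported times are about 3 weeks late. The documents do not support any of these. The first two depend on which reading was programmed. The third is an upper limit that rests on the earliest possible CA-125 date, and in the illustration it appears only at the 57% extreme.

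It is also true that the information is not lost. CA-125 response has its own table (14.02.02), Listing 16.02.02.03 includes time to CA-125 response, and the combined response tables are unaffected.

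**Conclusion.** The point holds as a stated rule that, taken literally, contradicts the endpoint it serves. The SAP leaves two readings open, and two programmers could produce different responder sets and dates. Section 15.1.7 also does not say which date applies when RECIST and CA-125 responses fall on different days.

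One route to exclusion is certain on the literal reading: progression or a new lesion more than 28 days from a CA-125 PR. The route through non-progressing lesions is probable only. The size is unknown and may be zero; the patient counts above rest on assumed response rates. The consequence is confined to one table and one graph, both descriptive, in one cohort of at most 37 patients. No hypothesis test, alpha or sample size depends on it, so it is a minor point.

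**What to change.** Replace the closing sentence of 15.1.7 with wording such as:

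> All combined responders per Table 5 are included. RECIST CR/PR and CA-125 response must each be confirmed by their own rule. The response date is the earlier of the first confirmed RECIST response and the CA-125 response date (15.1.2).

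If a RECIST-only analysis was intended, retitle Table 14.02.07 and Graph 14.02.05 to say so.

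The text change is one sentence, and the CA-125 response date should already be available from the derivation behind Listing 16.02.02.03. The SAP addendum (2.1) says that data to the 22 March 2021 cut-off have been reported under SAP version 4, and its output list does not repeat this analysis. In practice, therefore, add a note stating which rule was programmed, and rerun this one output if it was the literal rule.
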